4. STUDY DESIGN

This is an interventional pilot study based on the community stakeholder-derived data from three previous Quality Improvement projects to improve the partnership between CCHMC, CPS, and CHD to reduce the morbidity of childhood asthma in the inner city schools of Cincinnati and CCHMC. About 30 high-risk asthmatic participants will be identified to participate and a number of interventions will be incorporated including asthma specific questionnaires, use of a commercially available inhaler cap monitoring sensor, a mobile software management platform that tracks adherence of all asthma medications, mobile based telehealth medical visits to assess asthma control, and mobile based telehealth adherence problem-solving interventions.

This proposal is funded through a Luther Foundation and Verizon Foundation philanthropic gifts.

5. DURATION:

Duration for the participants will be 6 months. Participants will be enrolled in the study during the first year of the project. If necessary to complete enrollment the enrollment period will extend into the second school year. Data analysis will be performed 3 months after the last participant completes the project.

6. SELECTION & RECRUITMENT OF PARTICIPANTS:

A. Number of participants

Patient Population: 30 middle-schoolers/adolescents that attend a participating CPS (Oyler, Roberts, Withrow, and School of Creative and Performing Arts schools) will be recruited for a 6 month pilot study of testing the feasibility of a novel, school-based care delivery system to improve asthma outcomes. Given the relationship of the CCHMC Asthma Center with CPS and the CHD in our ongoing quality improvement work, the study investigators have contacts with the school staff, school nurses, and primary care providers associated with the following CPS (Oyler, Roberts, Withrow, and School of Creative and Performing arts). As part of this work, our team also helps the school nurses screen children with asthma to identify those with uncontrolled asthma and help the nurse's contact families to encourage them to establish or connect with an existing medical home to schedule an asthma visit and to obtain asthma medication.

B. Inclusion/Exclusion criteria

Inclusion

- age 10-17 years; history of provider-diagnosed asthma;
- history of uncontrolled asthma in the past 12 months (two ACT scores <20; ≥ 1 UC/ED visit or hospitalization for asthma, ≥ 2 prednisone bursts) with current persistent asthma as defined by NAEPP guidelines,

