There will be Post-Visit Surveys for subjects, parents and nurses that will be done periodically throughout the study. Survey participants will receive e-mails from the study team through RedCap for the surveys to be completed online directly into RedCap. The purpose of the surveys is feedback for effectiveness/satisfaction with the telehealth and propeller device. All participants who complete their response to the Post-Visit Surveys (subject, parent, school nurses) will receive \$10 added to their ClinCard. Nurses may be approached and asked follow-up questions regarding their perceptions of the study (see appendix X).

Visit 1- Baseline Medical Visit: This visit will be conducted in one of the following locations: the home, CCHMC, school nurse office or school-based health clinic, whichever location is more convenient for the family.

The coordinator will consent the parent/legal guardian(s) and obtain assent from the child/adolescent. Baseline questionnaires will be completed by a parent/guardian and participant and the study visits and procedures will be explained. A smart phone prepared by the CCHMC IT team with a data plan will be provided to the participant.

Basic asthma education will be provided. The study coordinator will conduct this visit. The participant will complete an Asthma Control Test (ACT) and the study coordinator will assist the participant to complete the TreatSmart program on a CCHMC secured laptop. The TreatSmart software web-based program, developed at CCHMC and hosted on a CCHMC secure server, will be used to determine the participant's symptom burden, health care utilization, systemic corticosteroid use, and current medication use to determine the level of asthma severity/control the participant has. The program also makes an initial treatment recommendation based on the National Asthma Education and Prevention Program (NAEPP asthma guidelines) if the participant's asthma meets the definition of persistent asthma and if their treatment dose should remain the same or be changed based on their level of control. This program will also produce a visit summary and asthma action plan. The TreatSmart program takes approximately 10 minutes to complete.

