Visit 2 - Visit 7: These visits will be conducted in one of the following locations: school nurse office, school conference room or school-based health clinic. These visits will occur at school or CCHMC over the lunch hour, during a study hall or non-core class, or afterschool. The study visits may be combined with school clinic visits with routine clinic care including vital signs and asthma assessments delivered by the school nurse or their assigned nursing students. Parent/guardian participation is not required for these visits. At visit 2, the coordinator will sync the Propeller app on the participant's cell phone and

the Propeller Health web platform with the inhaler caps so they and their family can see their inhaler use data for the rest of the study.

Each visit, the participants will be encouraged to use only the inhalers with the caps on them and given instructions to call the study team for replacements if they lose their medications.

After the baseline visit, 6 monthly medical Study Visits will be scheduled to assess the participant's level of asthma control and adjust the asthma medications as needed by the TreatSmart program using the same procedures as outlined above in the baseline medical visit.

Procedures done at these visits include:

- Questionnaires, ACT, TreatSmart
- Review of adherence from Propeller cap data
- Telehealth visit and medical evaluation
- Review of prescriptions and adjustment as needed
- Post-visit REDCap survey link will be emailed to the parent after medical visits 1 and 6 to solicit feedback on the telehealth visit to elicit feedback on participating in the study and use of the Propeller and telehealth technology.
- Post-visit REDCap survey link will be emailed to the child after the V2 and V6 medical visits and the first adherence visit to solicit feedback on the telehealth visit to elicit feedback on participating in the study and use of the Propeller and telehealth technology. The content of the survey is similar to the parent survey, The parent will be informed at the time they take the survey that a similar survey will be sent to their child and to contact the study team if they have questions or concerns about the survey content.

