- Post-visit REDCap survey link will be emailed to participating school nurses, nurse practitioners, and primary care physicians after medical visit 6 to elicit feedback on participating in the study and use of the Propeller and telehealth technology. School nurses or nurse practitioners may be approached and asked follow-up questions regarding their perceptions of the study (see appendix X).

Adherence/Self-Management Visits. These visits will occur at school or CCHMC over the lunch hour, during a study hall or non-core class, or afterschool in a private conference room, school nurse office or school-based health clinic as available. To minimize lost classroom time, these visits will be scheduled separately from the medical Study Visits. An adherence visit summary will be documented in the CCHMC medical record as a telehealth visit. Through our QI work, the school nurses and community primary care providers have read-only access of EPIC and can access these medical records after this visit. Parent/guardian participation is not required for these visits.

Starting at 6 weeks into the study, **every 2 weeks** the participant will receive **self-management visits** (total of 5) with the goal to improve inhaler adherence. The participant will meet with the CCHMC Adherence Health Psychology team investigators. Adherence data from the Propeller Health monitoring system will also be reviewed with the participant by the adherence specialist during adherence visits and the study coordinator during

medical visits. The study coordinator will help the participant connect to the Adherence team using the secure Telehealth Jabber software on the CCHMC laptop. The adherence specialist will also provide customized supportive text messages originating from the CCHMC email system to the participant's study phone. Text messages will not include personal health information, but instead will provide support and reminders related to adherence (e.g., Hello, remember to use your inhaler today!, Don't forget to put a reminder in your locker, Have you been using your monitoring log?).

A meal or snack will be provided to the participant.

Other:

PCP communication:

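### No survey is triggered by early exit, so late feedback on telehealth and Propeller will come from families retained to medical visit 6 and may overstate acceptability

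*Combined protocol and SAP*

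**What the plan says.** Section 4 gives the size of the pilot: "About 30 high-risk asthmatic participants will be identified to participate". Section 6A describes its aim as "testing the feasibility of a novel, school-based care delivery system to improve asthma outcomes".

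Section 8 introduces the surveys after the visit schedule: "There will be Post-Visit Surveys for subjects, parents and nurses that will be done periodically throughout the study". It adds: "The purpose of the surveys is feedback for effectiveness/satisfaction with the telehealth and propeller device". The procedure list under Visit 2 - Visit 7 then sets the timing for each group:

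- Parents: "Post-visit REDCap survey link will be emailed to the parent after medical visits 1 and 6 to solicit feedback on the telehealth visit".
- Children: "Post-visit REDCap survey link will be emailed to the child after the V2 and V6 medical visits and the first adherence visit".
- School nurses, nurse practitioners and PCPs: one survey, "after medical visit 6 to elicit feedback on participating in the study and use of the Propeller and telehealth technology". Nurses may also be asked follow-up questions, with no visit attached.

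The Section 8 schedule places Visit 2 at Month 1, the first self-management visit at Month 1½, Visit 6 at Month 5 and Visit 7 at Month 6. Families are blinded to the sensor data in the first month, and the platform opens to them at Visit 2.

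Section 6D allows withdrawal at any time, and Section 6C sets out tracing for participants lost to follow-up. The Study Termination and End of study paragraphs of Section 8 provide for a letter, refills and referral. None of these places mentions a survey.

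**The concern.** A feasibility pilot needs to hear from the families for whom the programme did not work. Burden, dislike of being monitored, or dissatisfaction with remote visits are all plausible reasons to stop. If the last survey goes out only after a visit late in follow-up, those who stopped before it are not asked at that point, and the late feedback describes those who stayed.

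The surveys are the plan's route to views on telehealth and the device. A favourable summary drawn mainly from retained families could shape decisions about the programme's next stage. The plan itself expects retention to be hard: Section 6C says so and lists many measures against loss, and Section 17 grades payments to keep families in.

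**Working it through.** **Step 1. What each group has been asked if the child leaves before medical visit 6.** This sets the survey timing beside the schedule, both in Section 8.

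| Group | Surveys offered before early exit | What they can cover |
|---|---|---|
| Parent | After Visit 1 | Precedes platform access at Visit 2 (Month 1), so not the live system |
| Child | After Visit 2, then after the first self-management visit | At Month 1½, about 1½ − 1 = ½ month of live use and 1 of 5 self-management visits |
| Nurse, nurse practitioner | None scheduled; optional follow-up questions | Still surveyed if another of their participants reaches visit 6 |
| PCP | None scheduled | Still surveyed if another of their participants reaches visit 6 |

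For a child, the interval with no scheduled survey runs from Month 1½ to Month 5, which is 3½ months.

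**Step 2. Is there a plan figure to reproduce?** No. The documents give no dropout rate, satisfaction threshold or survey analysis. Section 9 lists symptoms, ACT score, rescue use, exacerbations, absences, adherence and utilization, and no satisfaction outcome. What follows is illustration on assumed inputs.

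**Step 3. Would there be any leavers?** With N = 30 from the plan and an assumed dropout d before visit 6, the chance of at least one leaver is 1 − (1 − d)^30. This is 79% at d = 5%, 96% at 10%, and over 99.8% at 20% and 30%.

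**Step 4. How far could a stayers-only figure be from the all-enrolled figure?** Assume that every stayer answers and 90% are satisfied. With L leavers, of whom a share s are satisfied:

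all-enrolled satisfaction = [(30 − L) × 0.90 + L × s] / 30

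| L | s = 0.5 | s = 0.2 | Bounds, s from 0 to 1 |
|---|---|---|---|
| 3 | (24.3 + 1.5)/30 = 86% | (24.3 + 0.6)/30 = 83% | 24.3/30 = 81% to 27.3/30 = 91% |
| 6 | (21.6 + 3.0)/30 = 82% | (21.6 + 1.2)/30 = 76% | 21.6/30 = 72% to 27.6/30 = 92% |
| 9 | (18.9 + 4.5)/30 = 78% | (18.9 + 1.8)/30 = 69% | 18.9/30 = 63% to 27.9/30 = 93% |

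Against 90% among stayers, the overstatement is 4, 8 and 12 points at s = 0.5, and 7, 14 and 21 points at s = 0.2. With no leavers, or leavers as satisfied as stayers, it is 0. The upper bounds exceed 90%, so the design alone does not fix the sign.

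**The case against.** The strongest reply is that these are informal feedback surveys with no planned estimate, so nothing defined can be biased. That stands in part. A reader might infer that acceptability is overstated, or that an inflated result goes into the article and grant application named in Section 2. The documents support neither. Overstatement needs both early leavers and less satisfied leavers, and no figure is given for either. Section 2 does not say that survey percentages are carried forward.

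A reader might also infer that leavers are never heard. That is wrong for children who stay past Visit 2, who are surveyed then and, if they continue, after the first self-management visit, when the platform is live. It is too strong for nurses as well: about 30 children come from four schools, so a nurse with any retained participant still receives the survey, and follow-up questions are not tied to a visit.

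It is tempting to say that medical visit 6 is undefined, because Section 8 also speaks of six monthly visits after baseline, the sixth of which is Visit 7. But the Propeller text uses second study visit and second medical visit for the same occasion, and the child item says V6, which the schedule puts at Month 5. Counting from after baseline would also move the parent's first survey to Visit 2. The text therefore largely settles on Month 5.

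The retention measures in Sections 6C and 17 may keep losses small, and a survey sent to someone who cannot be reached will often go unanswered. Both points are fair. They limit the yield of an exit survey but do not supply one. Finally, the study visit table attachment and appendix X, both cited in the protocol, are not in the text available and could bear on survey timing or content.

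**Conclusion.** The gap is real but modest. As written, the last parent and child survey, and the only scheduled nurse and PCP survey, follow medical visit 6, and no form of early exit triggers one. Late feedback on telehealth and Propeller will therefore come from retained families and may overstate acceptability. The gap is widest for parents, whose only other survey comes before the platform is live. For children it is partial, and for nurses and PCPs it arises only where every participant in their care left early.

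Size and direction cannot be known from the documents. The 0 to 21 points in the working rest wholly on assumed dropout of 0 to 9 of 30, an assumed 90% satisfaction among stayers, and assumed satisfaction of leavers between 20% and 90%. The conclusion rests on the survey triggers, not on those figures, and would change if an attachment not seen here schedules an exit survey.

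**What to change.** Add one sentence to Section 8: the final child and parent survey, and the nurse and PCP survey for that participant, is emailed after Visit 6 (Month 5) or at withdrawal or study termination, whichever comes first, to those who agree to be contacted. At declared loss to follow-up, make one attempt. Keep the same $10 payment for the groups that Section 17 already pays. Name the visit as Visit 6 in all three survey items.

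Add one sentence to Section 9: survey responses are reported by retention status, with the number enrolled as the denominator and non-responders shown separately.

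The cost is one REDCap trigger and at most $10 each for child, parent and nurse, or $30 per leaver. For 9 leavers that is 9 × $30 = $270, which would have been payable had they stayed. No attendance is needed, since the surveys are completed online, and contact details are already collected under Section 6C. The downside is that some leavers will not reply, but the number missing is then visible.

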Previous studies indicate that a school-based asthma intervention with direct administration of asthma controller medication by a school nurse (Halterman 2011 and 2012) can improve asthma outcomes in children. Furthermore, the use of an innovative software sensor and interactive management platform, Propeller Health, in a community setting has also been shown to improve asthma outcomes in adults (Van Sickle 2013). However, the propeller platform has not been extensively tested in children or in the school setting. Up to 75% of adolescents 12-17 years and 85% of African-American children have access to a smartphone and over 80% of middle-schoolers have their own cell phone. Over 90 % of middle-schoolers and adolescents go online (ref: <http://www.pewinternet.org/2015/04/09/teens-social-media-technology-2015/>, <http://cdn.theatlantic.com/static/mt/assets/science/Research%20Findings%20MARC%202011%20Survey%20Grades%203-12.pdf>). 71% of adolescents use at least one social media web-site with Facebook, Instagram, Snapchat, Twitter, Google+, Vine, and Tumblr being the most popular (ref: <http://www.pewinternet.org/2015/04/09/teens-social-media-technology-2015/>).

Current infrastructure for implementing this project: The CCHMC Asthma Center in partnership with the CCHMC Anderson Center for Community Health, the CHD and CPS have an in-school asthma improvement initiative in place called the Asthma Control Test (ACT) screening program. This program provides asthma screening in the fall to CPS participants in the school setting by CHD school nurses and consultation support through the CCHMC Asthma Center. This program is driven and has oversight through the CCHMC Population Health Community Committee, a multidisciplinary group representing the various stakeholders. For this project, we would identify potential focus group participants through the ACT screening program and through participant sick visits to the school nurses for asthma related problems. To address the concern of high rate of pediatric asthma hospitalizations in Greater Cincinnati, we are embarking on an innovative QI-research pilot to develop “asthma-free schools” in neighborhoods where the incidence of asthma is especially high.

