The subject or the subject and his or her parent will be given the consent for the study and it will be reviewed and time given for questions. The subject will sign the assent or consent after all questions are answered and a signed copy of the consent form will be given to the subject to keep. The subject will be informed that this research is voluntary and that they are able to withdraw at any time. No study related procedures will be done prior to consent being signed.

For participants under age 18, age of assent will be determined by the IRB and those assenting will sign after all questions are answered.

For non-English speaking participants

Because this is a small pilot and heavily dependent on English fluency for teleconference interviews and questionnaires, only participants who are fluent in English will be enrolled. If a parent is non-English speaking, the PI will determine if the subject can be enrolled based on subject's fluency. If a non-English speaking parent will be giving Parental

Permission, the research team will use a short form consent process as per CCHMC SOP 41-1.8. The approved long consent form will serve as the summary of the research.

8. STUDY PROCEDURES:

Visit	Screening Phone call	Visit 1	Visit 2	Self-Management Visit 1	Visit 3	Self-Management Visit 2	Self-Management Visit 3	Visit 4	Self-Management Visit 4	Self-Management Visit 5	Visit 5	Visit 6	Visit 7	
Time		Day 1	Month 1	Month 1½	Month 2	Month 2	Month 2½	Month 3	Month 3	Month 3½	Month 4	Month 5	Month 6	
Place	H/CCHMC / SNO/ SHC			SNO/SHC	SNO/SHC	SNO/SHC	SNO/SHC	SNO/SHC	SNO/SHC	SNO/SHC				
Procedures														
Telehealth visit	x		x	x	x	x	x	x	x	x				
Motivational Interview			x	x	x	x	x	x	x	x				
Questionnaires	x	x		x				x			x	x	x	
Asthma education	x													
ACT	x	x		x			x			x	x	x		
TreatSmart (Web Based)											x	x	x	
Prescriptions as needed	x	x		x			x			x	x	x		
Review Smart Cap use		x		x			x		x		x	x	x	
Dispense smart phone and preloaded data plan	x													
Dispense propeller Health cap	x													
Propeller Health system education/load on smart phone			x											

H=Home
SNO=School Nurse Office
SHC=School Health Clinic

The study length is 6 months. 30 participants will be enrolled over 3 months during the 2015-2016 school year. Propeller, TreatSmart program and ACT screenshots are located in the Appendix.

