In addition, the CCHMC study team will receive a Propeller Health daily report of participants that have not taken their daily controller medication in the last 7 days, have changed their asthma symptoms control level, or have experienced a 200% increase in their rescue medication use in the past 24 hrs. The study team will communicate with both the school nurse and the participant to gather more information on the severity of their asthma symptoms using the Phone Call Exacerbation Form. If the participant is experiencing severe symptoms, they will be encouraged to be urgently evaluated by the school nurse, school-based health clinic, community primary care provider, or a local urgent care or emergency department.

Study Termination. During each medical visit, the number of severe asthma exacerbations [treated with \geq 4 days of systemic steroids; \geq 2 hospitalizations for asthma; \geq 1 PICU admission, intubation or hypoxic seizure due to asthma] since the start of the study will be determined. If the participant has \geq 4 severe asthma exacerbations, study participation will be ended. The procedures for the end of study will also be followed with the recommendation of referral to the CCHMC Difficult-to-Treat Asthma Clinic.

End of study. At the end of the study, the participant and their parents/legal guardians will be given a letter which summarizes which medication the participant was prescribed at the last month of the study. The study team will make sure that the participant has 2 additional refills at the end of the study. The letter will encourage them to make an appointment and visit their primary care physician within 2 months of the study end. Information on how to make an appointment at CCHMC Asthma Center will also be provided.

9. DATA ANALYSIS/METHODS:

Study Outcomes:

The adolescent's asthma outcomes and adherence will be measured at baseline and during the monthly medical visits for a total of 6 months. Outcomes will be measured during the monthly medical visits using a computerized TreatSmart program based on the NAEPP asthma guidelines which was adapted by the CCHMC Asthma Center database team from the Inner City Asthma Coalition (Appendix B), ACT scores (Appendix C), and Propeller Health web-based inhaler cap monitoring sensor and mobile software management platform (Appendix A).

Primary Outcome:

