Two-week histories of asthma symptoms measured per month (daytime symptoms, nighttime symptoms, or activity limitations) during the intervention period (from completion of the first month to study exit). The symptoms will be measured by a two-week recall of adolescent captured by the TreatSmart program.

Secondary Outcomes:

ACT score over past 4 weeks; rescue medication use (Propeller Health monitoring), oral-steroid requiring exacerbations questionnaires (2-week recall TreatSmart program); school absences (parent and subject report), adherence of controller medication (Propeller Health monitoring).

The asthma symptom burden, ACT score, exacerbation, healthcare utilization outcomes are commonly reported in both the adult and pediatric asthma literature, are endorsed by national asthma guidelines and the National Institutes of Health (NIH) asthma-outcome conference, and will also be measured.

Data Analysis

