We will use descriptive statistics to characterize the sample demographics. A descriptive analysis with calculation of means, medians, and standard deviations will be performed for each continuous measure; categorical measures will be examined with percentages. We used paired t-tests to evaluate the null hypothesis that there was no change in the primary outcomes (two-week histories of daytime symptoms, nighttime symptoms, or activity limitations) while participants are blinded to data collected by the Propeller medication sensor in the first month of participation. Nonparametric methods will be used if the assumptions for paired t-tests are violated. The primary analyses will test whether the school-based interventional program improves two-week histories of asthma symptoms measured per month (daytime symptoms, nighttime symptoms, or activity limitations) during the intervention period (from completion of the first month to study exit). Linear mixed effects models with a random effect for subject assessed changes in primary asthma endpoints across the five subsequent months of enrollment (at the completion of the first month, the second month, the third month, the fourth month and the fifth month upon exit) when participants will be able to access their usage data online. Participants with one or more observations will be included in the analysis. All statistical analyses will be implemented in SAS 9.3 (SAS Institute, Cary, NC) and use a significance level of 0.05. Potential confounders identified from the literature, such as age, gender, season of enrollment, severity of asthma at baseline, smoke exposure, history of allergic disease, will be adjusted in the analyses. The REML model used for these analyses requires that any missing data are "missing at random" (MAR) to yield valid estimates. In order to account for the presence of possible non-ignorable missing data, pattern-mixture modeling will be applied for these analyses.

The secondary analyses will look at the health system utilization, rescue medication use, adherence and lost school days. Linear mixed-effect models will be used to compare the continuous outcomes such as lost school days. Generalized linear mixed effect models will be used to compare the discrete outcomes such as health system utilization, both accounting for repeated measurement over time while adjusting for confounders.

Future use

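### Lost school days is analysed with no term for days school was open, so follow-up that runs into late spring or summer can look like programme benefit

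*Combined protocol and SAP*

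**What the plan says.** Section 9 lists the outcome among the secondary outcomes as "school absences (parent and subject report" and gives no period for it. The ACT entry beside it has four weeks, and the symptom and oral-steroid entries have two weeks. The TreatSmart screens in Appendix B contain no absence item.

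For the analysis, Section 9 says "Linear mixed-effect models will be used to compare the continuous outcomes such as lost school days", and separately "Generalized linear mixed effect models will be used to compare the discrete outcomes such as health system utilization". Both models account for repeated measurement and adjust for confounders. The adjustment list reads "Potential confounders identified from the literature, such as age, gender, season of enrollment, severity of asthma at baseline", followed by smoke exposure and allergic history. No school-day denominator, offset or time-varying calendar term is named.

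Outcomes are "measured at baseline and during the monthly medical visits for a total of 6 months". The five analysis time points in Section 9 (completion of Months 1 to 5) are given for the primary endpoints only, so it is not stated whether baseline or Month 6 enters the absence model.

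On timing, Section 8 says "30 participants will be enrolled over 3 months during the 2015-2016 school year", and Section 5 adds "If necessary to complete enrollment the enrollment period will extend into the second school year". No start month is given.

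**The concern.** A child can lose a school day only when school is open. The number of open days in a monthly interval falls at breaks and reaches zero in summer. A model for the raw count over study month attributes any such fall to time in the programme. No concurrent control group shares the calendar, so nothing in the design separates the two.

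Three months of accrual plus six months of follow-up is 3 + 6 = 9 months, about the length of a school year. Follow-up therefore stays clear of summer only if accrual starts early in the year. Missed school is part of the stated rationale (Sections 1 and 3), and Section 2 says the results will feed a journal article and a grant application. A spurious decline could carry over into both.

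**Working it through.** The plan gives no effect size, power or absence rate for this outcome, so there is no figure of its own to reproduce.

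**Inputs from the plan:** 30 children, 3-month accrual, monthly visits, a linear mixed model with a subject effect, and a significance level of 0.05 (taken as two-sided).

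**Assumed inputs:**
- A 182-day school year, 17 August to 25 May, with Thanksgiving, a two-week winter break, a one-week spring break and three single holidays.
- A constant absence rate per open day, 10% unless stated.
- 30-day recall, visits every 30 days, and entry at random on school days within a 3-month window.
- Gamma-Poisson counts (child and child-month variance 0.5 each), capped at open days.
- No programme effect. The main simulation used 2,000 runs per cell.

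**Step 1: expected counts.** Expected lost days = absence rate × open days. For January-March entry, mean open days in Months 1-5 are 19.7, 19.3, 15.9, 10.2 and 2.7. At 10% this gives 1.97, 1.93, 1.59, 1.02 and 0.27 lost days. The least-squares slope over five equally spaced months is Σ(t − 3)y / 10 = (−2×1.97 − 1.93 + 1.02 + 2×0.27) / 10 = −0.431 per month. From Month 1 to Month 5 that is 4 × (−0.431) = −1.72 days with no programme effect (simulated mean −1.71).

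**Step 2: can season of enrollment absorb this?** Write y = a + b·month + c·season(child) + u(child) + e. Season does not vary within a child, so with complete visits the estimate of b is the same with or without it. In simulation with September-April entry, adding the factor changed the false-positive rate from 25/31/36% to 24/31/36% at 5/10/15% absence.

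**Step 3: false-positive rate for a linear trend, Months 1-5, 10% absence.** Ranges span separate runs on the same assumed calendar.

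| Entry window | No-school intervals scored zero | Left missing |
|---|---|---|
| September-November | 5-6% | no such intervals |
| October-December | 8-9% | not tabulated |
| November-January | about 4% | not tabulated |
| December-February | 48-50% | 8-11% |
| January-March | 97-98% | 28-36% |

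**Step 4: sensitivity.**
- Absence of 5/10/15% gives 39/50/58% for December-February, scored zero.
- A different assumed calendar gives 43% (December-February) and 95% (January-March) at 10%.
- Adding Month 6 raises November-January from about 4% to about 24%, scored zero.
- A separate calculation used another calendar, 4-8% absence and six monthly reports. It gave 3-6% when accrual starts between 19 August and 1 October, 15-26% for 1 November and 92-99% for 1 December. These figures include Month 6, so they are not comparable with the table.

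**Step 5: the alternative.** The proportion of open days missed, in the same linear mixed model with at least 5 open days per interval, rejects in about 4-6% of trials in every window. An offset for log(days in session) was tested less. A negative binomial mixed model gave 5.0%, 7.3% and 4.7% in three windows (300 runs each; two fits failed in the 7.3% window). A Poisson GEE gave 4-11%.

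**Step 6: the opposite direction.** With October-December entry the winter break falls early, and mean open days are 17.9, 16.2, 16.9, 19.8 and 19.5. The false change is +0.28 days, and about nine in ten of the false positives are apparent worsening. For a true 40% fall, power is about 25-26% on raw counts against 43% on the proportion. With Month 6 added, the false-positive rate drops to 5-6% and the power gap narrows to 35% against 45%.

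**The case against.** The strongest reply is that the trial may never reach the damaging part of the calendar. Section 3 says of the existing asthma programme: "This program provides asthma screening in the fall to CPS participants in the school setting". Section 6 lists school screening first among its recruitment routes. Section 8 places visits around the school day, which presumes school is in session. If entry is in early autumn, raw counts behave well and the proportion costs some power. If closed intervals simply yield no report, the December-February figure falls from about 50% to about 8-11%. The confounder list is also open-ended, so an analyst could add a calendar term.

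Much of this stands, and it limits the size. It does not supply the missing term. Fall screening is one of five recruitment routes and fixes no start month. Section 5 allows enrolment into a second school year. Section 8 permits visits at the hospital, so a report covering a closed interval is possible. Leaving such intervals missing still gives 28-36% for January-March entry, because partly open intervals remain. An open list is no safeguard when the plan does not say that days in session will be collected.

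**Conclusion.** The concern holds in conditional form. The planned model for lost school days has no exposure term, and season of enrollment cannot stand in for one. If follow-up reaches late spring or summer, a false decline can appear. The rate runs from near nominal (September-November entry) to almost certain (January-March entry, no-school intervals scored zero). All of this rests on an assumed calendar and assumed absence rates. The size for this trial is unknown and may be small.

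Four stronger readings are tempting and are not supported:
- **That the trial has no absence recall window.** The reviewed text states none, but the questionnaires were not supplied and one may be printed there. A window alone would still not give a denominator.
- **That the trial's own result will be a false benefit.** No start month is given, and nothing says closed intervals would be scored zero.
- **That masking of a real benefit is an equal danger.** It is possible with October-December entry, but it is smaller and weakens when Month 6 is included.
- **That the linear model, or the primary symptom result, is at fault.** The same linear model works on the proportion. Symptoms can occur whether or not school is open, so this argument does not carry over to them.

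The outcome is secondary in a 30-child pilot. The change is worth making but not critical.

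**What to change.** In Section 9:
1. State the recall window for absences and which visits enter the lost-school-day model.
2. For each child and interval, take the number of school days in session in that window from the school calendar.
3. Exclude intervals with no or very few open days, with the minimum fixed in advance (for example, fewer than 5).
4. Analyse the proportion of open days missed in the linear mixed model already planned. Use a count model with log(days in session) as offset as a sensitivity analysis.

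The cost is wording plus a calendar lookup, and some lost data. With a 5-day minimum, about 0% of intervals are lost for September-November entry, 12% for December-February and 26% for January-March. If entry is in early autumn, power for an assumed 40% fall at 10% absence drops to about 42-46%, from 49-54% on raw counts. For January-March entry the proportion has about 23% power: the change removes the false trend but cannot restore information lost to summer.
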